#### **9.1.3 Suspected Unexpected Serious Adverse Reactions (SUSAR)**

An unexpected adverse event is defined as any adverse drug experience where there is evidence to suggest a causal relationship, the specificity or severity of which is not consistent with the Reference Safety Information (RSI) in the current LOAd703 and/or atezolizumab IBs.

Unexpected, as used in this definition, refers to an adverse drug experience that has not been previously observed (e.g., included in the IB) as opposed to the adverse drug experience not being anticipated from the pharmacological properties of the pharmaceutical product.

#### **9.1.4 Serious Adverse Reactions (SAR)**

A serious adverse reaction (SAR) is any AE for which there is evidence to suggest a causal relationship (reasonable possibility) between the study drug and the AE. By definition, all SARs are AEs, nevertheless, not all AEs are SARs. Both LOAd703 and atezolizumab are regarded as study drugs in this study.

#### **9.1.5 Non-Serious Adverse Event**

All AEs not fulfilling the previous definitions are classified as non-serious.

### **9.2 Evaluating and Documenting Adverse Events (AE)**

AEs are graded in the study according to the NCI Common Terminology Criteria for Adverse Events (CTCAE) version 5.0 (refer to <http://ctep.cancer.gov>). All AEs (except for grade 1 and 2 laboratory abnormalities that do not require an intervention) are to be recorded on the AE page in the eCRF and source documentation.

During [REDACTED], the Investigator will note the occurrence and nature of each patient’s existing medical condition(s). Occurrence and nature of AEs (including lab events) directly observed by the study personnel or spontaneously reported by the patient during the study will be reported. Each patient will be asked about AEs at each visit after the first dose of the investigational products LOAd703 and/or atezolizumab.

The general AE reporting period for this trial begins upon receiving the first LOAd703 and/or atezolizumab treatment and continues until final clinical follow-up visit at [REDACTED]

If both study treatments are prematurely discontinued, AEs should be recorded [REDACTED]

[REDACTED] see 4.4.1 Off-treatment patient).

If patients are prematurely withdrawn from the study and enter survival follow-up (i.e., survival follow-up patients), they will be followed for a minimum [REDACTED]

[REDACTED] (see 4.4.2 *Survival follow up patient*).

If a patient experiences an AE after signing the informed consent, but before treatment is started, the event will be recorded as an existing medical condition unless the Investigator believes that the event may have causal relationship to a study-specific procedure described in the protocol. If LOAd703 and/or atezolizumab have been administrated when an AE occurs, its relationship to the study drugs will be judged by the Investigator.

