### 3.4 Duration of Study

Timeline:	First patient in	Q3 2020
	Last patient's last visit	Q1 2024
	Study end	Q12024

After a screening period [REDACTED], each patient will receive a maximum of 12 LOAd703 injections (q3w) in combination with atezolizumab (q3w) after which supportive therapy with atezolizumab alone is continued until the final clinical visits (i.e. maximum 7 additional infusions). The patients will be scheduled for study visits until final clinical follow-up in study [REDACTED]

If both treatments are prematurely discontinued the final clinical follow-up visit could be scheduled earlier, [REDACTED]

In total, patients will visit the clinic regularly for a maximum 60-weeks ([REDACTED]). Thereafter only OS will be recorded every [REDACTED] whereby information will be collected via e.g. telephone calls (US) or medical records (SWE, US) until death or study end.

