## 5.2 Treatment Schedule for Study Visits

The LOAd703 treatment schedule and study visits over time are described in *Figure 1: Study timeline* and *14.1 Appendix I: Schedule of Events*. LOAd703 treatment is given up to 12 times. Atezolizumab will be administered continuously during study participation if judged beneficial and safe for the patient by the Investigator. In total, the patient can participate in study visits for 60 weeks (██████████). If patients are not on-treatment, the blue-labeled study visits for sampling are canceled. On-treatment patients refers to patients continuing LOAd703 and/or atezolizumab treatment. Patients discontinuing treatment (i.e., off-treatment) can have the final follow-up visit scheduled earlier. The final follow-up visit should be at least ██████████ so that the final endpoint data are collected. After the final follow-up visit at the clinic, patient health status and the overall survival will be recorded until death or End of Study, (see 7.5.3 Survival Follow-Up).

**Figure 1. Study timeline.** Schedule for study treatments, sampling, and follow-up visits. The planned study participation with visits to the clinic for an individual patient spans a maximum of 60 weeks ██████████) provided that either LOAd703 or atezolizumab is continued. Note that shedding samples will be collected ██████████ Further, atezolizumab PK sampling at ██████████ Following the final follow-up clinical visit, patient health status and overall survival will be recorded until death or End of Study (see 7.5.3 Survival Follow-Up).

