## **5.8 Approved and Non-Approved Concomitant Treatment**

Patients can receive full supportive care while on this study.

[REDACTED]

[REDACTED]

[REDACTED]

[REDACTED]

[REDACTED]

[REDACTED]

Live, attenuated vaccines (e.g., FluMist®) are prohibited within 4 weeks prior to initiation of study treatment, during treatment, and for 5 months after the final dose of atezolizumab and/or LOAd703.

Adenovirus-based vaccines (e.g., Vaxzevria, known as COVID-19 vaccine Astra Zeneca, J&J Covid-19 vaccine) are prohibited 3 months prior to initiation of study treatment, during treatment and 6 months after the final dose of LOAd703.

Need for palliative surgery as well as palliative local radiotherapy, e.g., for brain or bone metastasis, during the trial is accepted unless this prohibits tumor evaluation according to the RECIST-criteria.

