### **7.5.3 Survival Follow-Up**

After the final clinical follow-up visit at the clinic, overall survival (OS) will be recorded [REDACTED] [REDACTED]. OS will be collected until the trial is closed, i.e. until LPLV. OS may be collected via medical records (Sweden, US) or by telephone/email (US) from the Investigator or research nurse/research coordinator to the patient and will consist only of questions regarding the patient's health. If the patient is initiating another anti-cancer treatment, the treatment will be documented if the information is available, since it may affect the OS. The day of death will be documented.

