#### **7.7.4      Deaths, Other Serious Adverse Events, and Other Significant Adverse Events**

All deaths during the study, including the post treatment follow-up period, will be listed by subject, to include the primary cause of death. Serious AEs and other significant AEs, including those that led to withdrawal, interruption, or dose reduction of the study drug, will be provided in separate subject data listings.

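### For patients who receive the last scheduled atezolizumab infusion, general AE reporting closes at most 6 weeks later, no readable provision collects related events after that, and the SAP needs a cause of death that Protocol 7.5.3 does not record

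*Protocol*

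**What the plan says.** **End of AE reporting.** Protocol 9.2 starts general AE reporting at the first dose of either drug, and it "continues until final clinical follow-up visit at" a week that is blacked out. SAP 6.4.1.2 repeats the rule. Patients who stop both drugs early, or who enter survival follow-up, have separate windows whose lengths are redacted.

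**Treatment and visits.** Protocol 3.4 allows up to 12 LOAd703 treatments at 3-week intervals, each paired with an atezolizumab infusion. For the period that follows, it states that "supportive therapy with atezolizumab alone is continued until the final clinical visits (i.e. maximum 7 additional infusions"). The same section caps clinic visits at 60 weeks. Protocol 5.1 and 6.3 say that missed or delayed doses are not made up.

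**After the final visit.** Protocol 3.4 restricts collection to overall survival. Protocol 5.2 says that "patient health status and the overall survival will be recorded until death or End of Study". Protocol 7.5.3 describes record reviews, or telephone or email contacts, with questions about the patient's health. Protocol 5.1 gives a 4-month interval and ties it to a specific consent question.

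**Deaths.** Protocol 7.5.3: "The day of death will be documented". SAP 7.7.4: "All deaths during the study, including the post treatment follow-up period, will be listed by subject, to include the primary cause of death".

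**A post-dose precaution.** Protocol 5.8 prohibits live vaccines "during treatment, and for 5 months after the final dose of atezolizumab and/or LOAd703".

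**The concern.** Safety is the primary endpoint, Protocol 9.0 treats both drugs as experimental, and Protocol 2.6.1 itself raises the possibility of added risk from pairing two immunotherapies. A patient who stays on atezolizumab to the end of the schedule reaches the close of AE reporting soon after the last infusion. An immune-related event that appears later may be mentioned at a survival contact, but no readable text says that it becomes an AE or serious AE (SAE) record.

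Deaths raise a second difficulty. The SAP promises a cause for each follow-up death, yet the section that governs survival follow-up names only the date. Attribution to LOAd703 or atezolizumab is defined in Protocol 9.2.2 for AEs. A death after AE reporting has closed therefore has no stated route to a related or unrelated classification. The readable SAP does not tell the reader of the safety tables that collection closes at this point.

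**Working it through.** This is schedule arithmetic, followed by a comparison of sections. The documents print no figure for the gap, and the 60 weeks cannot be rebuilt because its bracketed breakdown is redacted.

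1. **Last infusion.** Inputs from Protocol 3.4: 12 combined doses, "maximum 7 additional infusions", and a 3-week interval. Infusions = 12 + 7 = 19. With the first at week 0 (an assumption; Protocol 4.3 does refer to a week 0 visit), the last is at (19 − 1) × 3 = week 54. Because missed doses are not made up, this slot stays at week 54 even for a patient who skipped one earlier.

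2. **AE follow-up after it.** If the final visit is at week 60, the gap is 60 − 54 = 6 weeks. If the 60 weeks include 3 weeks of screening (assumption), the final visit is at week 57 and the gap is 57 − 54 = 3 weeks. A first infusion later than week 0 would shorten the gap further. Six weeks is therefore the maximum for a patient who receives the last scheduled infusion.

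3. **Who this covers.** If AE visits run to week 60, a last infusion at week 51 leaves up to 60 − 51 = 9 weeks, and one at week 36 leaves up to 60 − 36 = 24 weeks. The 6-week limit is not general, and the actual windows for early stoppers are redacted.

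4. **A benchmark.** The 5-month vaccine restriction equals 5 × 4 = 20 weeks by the protocol's definition of a study month, or 5 × 365.25 / 12 / 7 = 21.7 calendar weeks.
   - 6-week gap: covers 6 / 21.7 = 28% to 6 / 20 = 30%, leaving 14.0 to 15.7 weeks.
   - 3-week gap: leaves 17.0 to 18.7 weeks.

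5. **Where the first survival contact falls.** Four months is 4 × 4 = 16 weeks in study months, or 4 × 365.25 / 12 / 7 = 17.4 calendar weeks. Counted from a final visit 3 to 6 weeks after the last infusion, the first contact comes 3 + 16 = 19 to 6 + 17.4 = 23.4 weeks after that infusion. That is near the end of the benchmark window, so one existing contact could look back over nearly all of it.

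6. **Sections side by side.**
   - Protocol 3.4 (survival alone) does not agree with Protocol 5.2 and 7.5.3 (health as well).
   - Protocol 7.5.3 (day of death) does not supply what SAP 7.7.4 needs (primary cause).
   - SAP 7.7.3 sets no end date for TEAEs, so the practical cut-off is whatever Protocol 9.2 collects.

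**The case against.** The strongest reply is that much of the relevant text cannot be read. The sentence in Protocol 9.2 breaks off at a redaction, parts of 9.3.1 and 7.5.3 are blacked out, and the plan for immunological AEs listed in the contents as 9.4 does not appear. The readable SAE notification text has no end date, 7.2.13 describes AE monitoring as continuous through the trial, and the TEAE definition would admit any later event that was recorded. This stands: one can say only that no readable provision collects these events.

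Three stronger readings are tempting and are not supported.

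- *That the plan regards patients as exposed for 5 months.* The 5 months is a live-vaccine rule that covers either drug. Other windows differ: 6 months after LOAd703 for adenovirus-based vaccines, and contraception during study treatment (7.2.12). It can serve as a benchmark but is not a stated exposure window.
- *That related deaths go unreported.* Date of death is collected and SAP 7.7.4 lists every death. What is missing from readable protocol text is the cause, and the attribution, of deaths after the final visit.
- *That the longest-treated patients have the shortest AE follow-up.* This comparison needs the redacted windows for early stoppers.

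It is also fair to say that the affected group may be small. Patients leave treatment for confirmed progression or toxicity, and the number who reach week 54 is not stated, so no size can be put on any understatement of late events.

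**Conclusion.** The point holds for patients who receive the last scheduled infusion. Their general AE reporting closes at most 6 weeks afterwards, or about 3 weeks if the 60 weeks include a 3-week screening period. This rests on a first infusion at week 0 and a strict 3-week schedule. Whether later related events are collected elsewhere cannot be settled from the readable text.

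Two mismatches do not depend on any choice of window: 3.4 against 5.2 and 7.5.3 on what is recorded after the final visit, and 7.5.3 against SAP 7.7.4 on cause of death. As far as the readable text goes, the cause-of-death listing promised in the SAP has no stated data source for deaths after the final visit. This is a gap that can be closed cheaply in the primary safety endpoint. It does not invalidate the safety analysis.

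**What to change.** In Protocol 9.2 and 7.5.3, use the survival contacts and record reviews already planned to record:

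- SAEs and immunological AEs at least possibly related to either drug, for a post-dose window that the sponsor states and justifies;
- the cause of each death;
- the relation of each death to LOAd703 and to atezolizumab separately.

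If a redacted passage already sets a later SAE window, state it openly and carry it into the SAP. Reconcile Protocol 3.4 with 5.2 and 7.5.3, and Protocol 7.5.3 with SAP 7.7.4. In SAP 7.7.3 and 7.7.4, tabulate events found after the final visit separately from TEAEs, with the number of patients who actually had a contact or record review within the window.

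The cost is a small amendment and a few entries at contacts already scheduled; no treatment rule changes. The limits should be stated with the table: telephone and record review find fewer events than clinic visits, the 4-month contact depends on a consent question, and the last patients will have no contact because follow-up ends at the last patient's last visit.

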### **9.2.1 Severity Grading**

The Investigator must determine the intensity of any AEs according to the NCI CTCAE Version 5.0 (see <http://ctep.cancer.gov>) and the causal relationship. Those AEs not covered by these criteria will be graded as follows:

1. **Mild**: Discomfort noticed, but no disruption of normal daily activity. Prescription drug not ordinarily needed for relief of the symptom but may be given because of the patient's personality/character.
2. **Moderate**: Discomfort sufficient enough to reduce or affect normal daily activity. Patient is able to continue in the study; treatment for the symptom may be needed.
3. **Severe**: Incapacitating, severe discomfort with inability to work or to perform normal daily activity. Severity may cause cessation of treatment with test drug; treatment for symptom may be given and/or patient hospitalized.
4. **Life-threatening**: Symptom(s) place the patient at immediate risk of death from the reaction as it occurred; does not include a reaction that, had it occurred in a more serious form, might have caused death.
5. **Fatal**: Event caused the death of the patient.

### **9.2.2 Attribution Definitions**

The Investigator will attempt to assess the relationship of the event to the study drugs separately. An AE is considered to be associated with the use of any or both of the investigational products if the attribution is determined as possible, probable or definite. Attribution of AEs will be recorded in the CRF as:

- **Unrelated**: The AE is clearly NOT related to LOAd703 (or atezolizumab).
- **Unlikely**: The AE is doubtfully related to LOAd703 (or atezolizumab).
- **Possible**: The AE may be related to LOAd703 (or atezolizumab).
- **Probable**: The AE is likely related to LOAd703 (or atezolizumab).
- **Definite**: The AE is clearly related to LOAd703 (or atezolizumab).

Attribution will be specified for LOAd703, atezolizumab, treatment procedure (i.e., intratumoral injection and/or intravenous infusion), disease or other.

### **9.2.3 Duration of Event**

The date of onset (and time if relevant), change of severity and the duration of the AE (i.e., date of resolution) will be recorded. Events that are ongoing at the time the patient completes follow-up will be documented as ongoing.

#### **9.2.4 Action(s) Taken Regarding the Study Drugs**

The method used to treat the AE, specifically any action taken with the study drugs, should be recorded. This includes, but is not limited to e.g., "dose reduced" or "discontinued".

### **9.3 Reporting Serious Adverse Events (SAE), Deaths, Unexpected AEs and DLTs**

#### **9.3.1 Reporting to Sponsor**

AEs classified as serious require expeditious handling and reporting to the CRO as the Sponsor's representative, to comply with regulatory requirements. The Sponsor and its designees must be notified immediately (within 24 hours of becoming aware of the event) by email or telephone. Notification by email is preferred. The email and telephone numbers listed below may be used.

Initial notification via telephone or email does not obviate the need for the Investigator to provide a completed SAE form/eCRF entry within the designated reporting time frames.

[REDACTED]

The completed Serious Adverse Event Report Forms are submitted by email to [REDACTED] within 24 hours of becoming aware of the event.

The SAE form and detailed instructions describing the procedure for reporting SAEs are found in the Investigator's Site File.

[REDACTED]

Email: [REDACTED]  
Phone: please see the Investigator Site File

#### **9.3.2 Safety Report – Reporting by Sponsor**

The Sponsor is responsible for submitting safety reports to the relevant regulatory authorities and ethics committees of any Suspected, Unexpected Serious Adverse Reactions (SUSARs). A SUSAR that is fatal or life-threatening should be reported as soon as possible, not later than 7 calendar days after the Sponsor becomes aware of the SUSAR, and with a follow-up report within another 8 days. Any other SUSARs should be reported within 15 days.

##### **9.3.2.1 MPA/EMA Safety Report (EU)**

The Sponsor is responsible for submitting safety reports to the MPA/EMA and IEC and this will be delegated to the CRO. A SUSAR that is fatal or life-threatening should be reported as soon as possible, not later than 7 calendar days after the Sponsor becomes aware of the SUSAR, and with a follow-up report within another 8 days. Any other SUSARs should be reported within 15 days.

SAEs that do not require expedited reporting should be listed together with SUSARs in the annual drug safety update report (DSUR), written by the Sponsor and submitted to the relevant regulatory authorities and ethics committees according to current legislation.

##### **9.3.2.2 IND Safety Report (US)**

Under Title 21 Code of Federal Regulation (CFR) Part 312.32, the Sponsor (or designee) is required to notify the FDA ([REDACTED]) and all participating Investigators (i.e., all Investigators to whom the Sponsor is providing drug under its IND or under any Investigator's IND) of any of the following:

Any SAR, that is both serious and unexpected, and if there is evidence to suggest a causal relationship between the study drug and the event, such as:

- A single occurrence of an event that is uncommon and known to be drug related.
- One or more occurrences of an event that is not commonly associated with the drug but is otherwise uncommon in the population exposed to the drug.
- An aggregate analysis of specific events observed in a clinical trial that indicates those events occur more frequently in the drug-treatment group than in a concurrent or historical control group.

In addition, the Sponsor must report the following:

- Any findings from epidemiological studies, pooled analysis of multiple studies, or clinical studies, whether or not conducted under an IND and whether or not conducted by the Sponsor, that suggest a significant risk in humans exposed to the drug.
- Any findings from laboratory animals or *in vitro* testing, whether or not conducted by the Sponsor, that suggest a significant risk in humans exposed to the drug, such as reports of mutagenicity, teratogenicity, or carcinogenicity, or reports of significant organ toxicity at or near the expected human exposure dose.
- Any clinically important increase in the rate of a serious suspected adverse reaction over that listed in the protocol or IB.

SAEs that do not require expedited reporting should be listed together with SUSARs in the annual DSUR, written by the Sponsor and submitted to the relevant regulatory authorities and ethics committees according to current legislation.

### **9.3.3 Reporting to IEC/IRB**

Investigators must report SAEs and AEs to his/her IRB or IEC per institutional guidelines and/or other applicable guidelines.

### **9.3.4 Procedures in Case of Medical Emergency**

The Investigator should ensure that the necessary procedures and expertise are available to cope with any emergencies during the study.

If an emergency occurs, please notify [REDACTED]

Email: [REDACTED]

Phone: please see the Investigator Site File

A high-contrast, black and white image showing a series of horizontal bars. The bars are mostly black, with white gaps between them. The bars are of varying lengths, creating a stepped or jagged pattern across the frame. The image is oriented vertically on the page.

## 9.5 Handling of Pregnancy

Any pregnancy diagnosed during the study participation must be reported immediately to the Sponsor. Women of childbearing potential and male with a partner of child bearing potential, will be thoroughly informed about contraceptive medication (see section 7.2.12 Concomitant Medications) before trial participation and to immediately inform the Investigator if pregnancy should occur during study participation. Pregnancy, in and of itself, is not regarded as an AE, unless there is suspicion that study medication may have interfered with the effectiveness of a contraceptive medication. If the patient becomes pregnant while participating in the study, the study drugs should be immediately discontinued. Pregnancy information about a female patient or a female partner of a male patient should be reported immediately from the time the Investigator first becomes aware of a pregnancy or its outcome. This will be performed by the Investigator by completing a Pregnancy Form.

Any pregnancy complication, spontaneous abortion, elective termination of a pregnancy for medical reasons, outcome of stillbirth, congenital anomaly/birth defect, or SAE in the mother will be recorded as an SAE and reported.

